Randomized controlled trial comparing covered metal stents versus uncovered metal stents for palliative biliary decompression in inoperable malignant distal bile duct obstruction

Participating centers:

Vanderbilt University Medical Center

Principal Investigator:

[name] MPH

Version Date: September 23, 2019

Background:

Endoscopic retrograde cholangiopancreatography (ERCP) with transpapillary placement of an endoprosthesis is an established intervention for palliation of malignant distal extrahepatic bile duct obstruction. Such intervention may provide relief of jaundice and pruritus, reduce the risk of ascending cholangitis, and permit administration of systemic chemotherapy. Plastic biliary stents are prone to stent occlusion and malfunction, with median stent patency duration of 12 weeks for 8 French gauge stents and 32 weeks for 10 French gauge stents¹, and therefore require repeat intervention via ERCP for stent removal and exchange every several months. The need for repeat intervention may require interruption of ongoing chemotherapy, may be otherwise undesirable from a patient perspective, and may have cost implications. Indeed, the goal of endoscopic biliary decompression should be to provide durable biliary drainage—ideally extending for the duration of the patient’s overall survival—in a single intervention.

Self-expanding metal biliary stents (SEMS) offer an internal diameter up to 10 mm, offer more durable biliary drainage compared to plastic stents^{2,3}, and have therefore become the endoprosthesis of choice for palliation of inoperable malignant distal bile duct obstruction. Variations in SEMS design exist, however, and the choice of ideal SEMS is uncertain—uncovered SEMS (U-SEMS) consist of a bare metal scaffold which may be prone to hyperplastic tissue ingrowth and stent occlusion; alternatively, covered SEMS (C-SEMS) feature a polyurethane coating which may prevent tissue ingrowth but which may increase the likelihood of inadvertent stent migration. A prior randomized controlled trial of a stainless steel U-SEMS versus a stainless steel partially covered C-SEMS revealed no difference in time to recurrent biliary obstruction⁴; and a recent meta-analysis demonstrated no clear advantage of C-SEMS vs U-SEMS⁵.

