Due to variations in stent material, design, and manufacture, however, such data may not be generalizable to current generation metal stents, which feature a nickel titanium alloy scaffold and which, in C-SEMS version, offer a full rather than partial polyurethane coating.

Hypothesis:

We hypothesize that current generation C-SEMS offer more durable biliary drainage and will decrease the need for biliary reintervention compared to U-SEMS in patients with inoperable malignant distal bile duct obstruction.

Objectives:

Primary objective: Compare the rate of long-term stent failure, defined as need for repeat biliary intervention (endoscopic, percutaneous, or surgical) following placement of C-SEMS vs U-SEMS for palliation of inoperable malignant distal bile duct obstruction.

Secondary objective: Compare the rate of adverse stent-related or intervention-related outcomes (pancreatitis, cholangitis, cholecystitis, perforation) following placement of C-SEMS vs U-SEMS for palliation of inoperable malignant distal bile duct obstruction.

Design:

Single-center prospective randomized controlled trial.

Inclusion criteria:

- Patients with distal bile duct obstruction due to pancreatic cancer, cholangiocarcinoma, or metastatic malignancy with a confirmed tissue diagnosis referred for ERCP with intended palliative metal stent placement for palliation of jaundice
- Patients 18 years of age and older
- Serum bilirubin > 2 mg/dL

Exclusion criteria:

- Prior endoscopic or percutaneous biliary drainage
- Post-surgical anatomy (ie pancreaticoduodenectomy, Billroth-type gastrectomy, Roux-en Y hepaticojejunostomy)
- Primary site of biliary obstruction involving the common hepatic duct or hilum
- Tumor involving gastric outlet, duodenum, or ampulla either precluding endoscopic access to the papilla or otherwise preventing endoscopic biliary cannulation
- Inability to provide written informed consent

Procedure:

- Patients will undergo ERCP under either MAC/general anesthesia or conscious sedation per institutional standard of care.

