- Following endoscopic biliary cannulation and diagnostic cholangiography, performed per standard of care, a sealed envelope will be opened to determine patient randomization to either a 10 mm diameter C-SEMS (Wallflex, Boston Scientific) or a 10 mm diameter U-SEMS (Wallflex, Boston Scientific). Due to the nature of the intervention, the proceduralist will not be blinded to study allocation. The choice of a 40 mm or 60 mm stent length will be at the discretion of the proceduralist.
- Post-procedure monitoring and discharge will be performed per institutional standard of care.

Follow-up:

- Day 1 follow-up for assessment of post-procedural adverse events will be performed by telephone call by an endoscopy post-assessment nurse (for outpatients) or by physician assessment at the patient's bedside (for inpatients), as per current institutional standard of care
- Follow-up will occur every 60 days by review of the electronic medical record or patient self-report to assess for primary and secondary study outcomes

Major treatment outcomes:

- Primary outcome: Performance of repeat ERCP, percutaneous biliary drainage, or surgical biliary bypass for palliation of persistent or recurrent biliary obstruction.
- Secondary outcomes: pancreatitis requiring hospital admission; cholangitis requiring hospital admission and intravenous antibiotics; cholecystitis requiring percutaneous, surgical, or endoscopic intervention; perforation.

Sample size and planned statistical analysis:

Retrospective data from VUMC has identified a long-term 25% failure rate of U-SEMS and 0% failure rate of C-SEMS when placed for palliation of malignant distal bile duct obstruction⁶. Assuming a somewhat more conservative estimate of durability rates, a sample size of 96 patients (48 per treatment arm) would be required to detect a 20% difference in stent failure rates at 80% power with an alpha level of 0.05. Also anticipating a 20% rate of dropout/loss to follow-up, the goal would be to enroll and randomize 116 total patients in the study.

Fisher's exact test will be used to assess the statistical significance in proportion of primary and secondary study outcomes, respectively. Additional univariate and multiple variable logistic regression analysis will be used to identify potential predictors of stent failure, to be reported including odds ratio and 95% confidence intervals. A two-sided P value of <0.05 will be the threshold for statistical significance in all cases.

Role of industry:

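### Long-term stent failure is tested as a crude proportion by Fisher's exact test, with no time horizon, data cut-off or rule for the anticipated 20% lost

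*Combined protocol and SAP*

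**What the plan says.** The Background sets the goal as durable drainage in a single intervention, "ideally extending for the duration of the patient’s overall survival", and cites an earlier randomised trial that "revealed no difference in time to recurrent biliary obstruction". The Hypothesis is that "current generation C-SEMS offer more durable biliary drainage and will decrease the need for biliary reintervention compared to U-SEMS". The primary objective is the rate of long-term stent failure; no duration is attached to that term.

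Under Major treatment outcomes, the primary outcome is "Performance of repeat ERCP, percutaneous biliary drainage, or surgical biliary bypass for palliation of persistent or recurrent biliary obstruction", again with no time window.

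Under Sample size and planned statistical analysis, Fisher's "exact test will be used to assess the statistical significance in proportion of primary and secondary study outcomes". Logistic regression is added to look for predictors of failure and has no time element either. The anticipated 20% dropout is used only to raise enrolment from 96 to 116. The planning rates are introduced by "Assuming a somewhat more conservative estimate of durability rates" and then not given; only a 20% difference is.

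On schedule, the Follow-up section says "Follow-up will occur every 60 days by review of the electronic medical record or patient self-report", while the form in Appendix A is completed at day 30 and at 30-day intervals after that. Neither gives an end. The form asks yes/no whether each type of reintervention has occurred since stent placement, and it records days to death.

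**The concern.** A proportion reintervened is a defined quantity only if everyone is observed for the same time, or until reintervention or death. The plan requires neither. A patient enrolled shortly before closure and still alive would count the same as one followed to death. The reported rate would then depend on the date the study closes, which the plan does not fix, and on whether the lost patients are dropped or counted as non-failures, which it does not say.

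What is at stake is the meaning of the primary result and possibly a smaller observed difference. A rate without a time unit also cannot readily be set beside results expressed as time to recurrent obstruction.

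**Working it through.** **1. The plan's own sample size.** Inputs from the documents: 20-point difference, two-sided 0.05, 80% power, 48 per arm, 116 randomised, 20% loss. The arm rates are not given, so 25% v 5% is assumed here (the retrospective U-SEMS rate less 20 points).

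Pooled-variance formula, mean rate 0.15:
n = [1.96 × √(2 × 0.15 × 0.85) + 0.842 × √(0.25 × 0.75 + 0.05 × 0.95)]² / 0.20² = 48.84, or 49 per arm, close to the stated 48.

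Exact two-sided Fisher power by full enumeration at 48 per arm:
- 22.5% v 2.5%: 80.8%
- 25% v 5%: 72.2%
- 30% v 10%: 61.3%

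At 25% v 5%, Fisher needs 55 analysed per arm for 80%. It has 82.9% if all 58 per arm are analysed at unchanged rates, and 72.1% at 46 per arm (116 × 0.8 = 92.8). The stated 80% is therefore reproducible, but under different pairs for different tests.

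**2. Effect of the closing date.** Assumptions, none given in the documents: uniform accrual over A = 36 months, exponential hazards, median survival m of 4, 6 or 9 months, no loss, lifetime failure p of 25% (U-SEMS) and 5% (C-SEMS). With death hazard μ = ln 2 / m, a failure hazard of μp/(1−p) gives lifetime risk p. The total hazard is h = μ/(1−p). If the study closes f months after last enrolment:

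observed proportion = p × {1 − [e^(−hf) − e^(−h(f+A))] / (hA)}

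For m = 4, f = 0: U-SEMS h = 0.2310, giving 25 × 0.880 = 22.0%; C-SEMS h = 0.1824, giving 5 × 0.848 = 4.2%; difference 17.8 points.

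| Close after last enrolment | m = 4 | m = 6 | m = 9 |
|---|---|---|---|
| 0 months | 17.8 | 16.6 | 15.0 |
| 6 months | 19.5 | 18.8 | 17.4 |
| 12 months | 19.9 | 19.6 | 18.7 |

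(Observed difference in points; true lifetime difference 20.)

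**3. How much of this belongs to the planned method.** Simulated trials of 58 per arm, about 20% lost, other assumptions as in step 2. The share of trials in which significance differs between closing at 0 and at 12 months, for m = 4, 6, 9:
- Fisher on completers: 10.2, 12.9, 16.7%
- log-rank on all 116: 7.5, 10.2, 12.4%
- chi-square on all 116: 7.7, 10.6, 12.8%

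About three-quarters of the Fisher figure remains under log-rank (7.5/10.2 = 74%, 10.2/12.9 = 79%, 12.4/16.7 = 74%).

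**4. The unwritten loss rule.** Dropping the lost patients or counting them as non-failures changes Fisher significance in 4 to 6% of simulated trials. Of 50 tables checked (6–15 v 0–4 failures, 46 or 58 per arm as denominators), only 9 v 2 changes: p = 0.0499 v 0.0531. That is a borderline illustration.

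**5. Power of the alternatives.** Nine scenarios (m = 4, 6, 9; complete follow-up, or closing 6 or 0 months after accrual), 25% v 5%, 20% loss:
- Fisher on completers: 60.3–75.5%
- Fisher on all 116: 55.2–73.2%
- chi-square on all 116: 69.8–82.9%
- log-rank on all 116: 71.9–85.3%

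Log-rank exceeds Fisher on completers by 8.7 to 11.6 points and chi-square on all 116 by 1.0 to 2.9. Keeping all patients does not by itself rescue Fisher; the gain comes mainly from a less conservative test on all 116. With equal rates of 15%, the rejection rates were 4.9% (log-rank), 4.9% (chi-square) and 2.9% (Fisher on completers).

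**The case against.** The best defence is that a proportion suits the question. The goal is drainage for the rest of life in one intervention, the retrospective benchmark (25% v 0%) is itself a proportion, and in a population with short survival most patients will reach reintervention or death if the study stays open long enough. On the assumed figures, closing twelve months after last enrolment leaves at most 1.3 points of the 20 unseen. This stands, but only given a follow-up commitment that the plan does not make. It supports the fixed-horizon proportion as an acceptable alternative.

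It is also fair that time-to-event analysis adds little power through time itself, that most of the closing-date sensitivity remains under log-rank, and that the loss rule seldom changes the result. All three stand. The case rests on defining the quantity to be estimated.

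On deaths, the outcome is the performance of a reintervention, so a patient who dies without one is most naturally a non-failure. The plan should say so, but the gap is smaller than that for losses.

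A reader might infer that the trial is underpowered or its size wrong. The documents do not support that: 22.5% v 2.5% fits the stated 80% for Fisher's test, and nothing says which pair was used. Nor can it be said that the form lacks a reintervention date, because its text is cut off.

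**Conclusion.** The concern holds in this form: the primary comparison is a proportion with no horizon, cut-off or loss rule, set against an objective about long-term durability. These gaps are read directly from the text and do not depend on any assumption.

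The size does. A 20-point lifetime difference would be seen as 15.0 to 17.8 points if the study closed at last enrolment and 18.7 to 19.9 points twelve months later, given assumed 36-month accrual, exponential hazards, median survival of 4 to 9 months and rates of 25% v 5%. Dilution is therefore conditional on an early close, which the plan neither states nor rules out.

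A reader might infer bias in favour of one stent, or that Fisher's test is the cause of the closing-date sensitivity. Neither follows: the arms are randomised with the same follow-up rules, and most of that sensitivity is common to any analysis of the same data. The point should be fixed; it does not invalidate the design.

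**What to change.** - State a data cut-off and a minimum follow-up.
- Make the primary analysis time from stent placement to first reintervention in all randomised patients: log-rank with a cause-specific hazard ratio and 95% CI, censoring at last contact and at death. Report with it the cumulative incidence of reintervention at fixed times, for example 6 and 12 months, with death as a competing event.
- Alternatively, keep a proportion as primary, but at a fixed horizon and with a written rule for deaths and losses.
- Record the date of each reintervention if the form does not already do so.
- Minor: state the two planning rates and restate the power for the test actually used. Reconcile the 60-day interval in the Follow-up section with the 30-day interval in Appendix A.

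The cost is rewording the analysis section, slightly more analysis work and, at most, one date per reintervention from records already being reviewed. The hazard ratio must be read with the cumulative incidence, because it is not by itself a patient's chance of a second procedure. Censoring at last contact assumes that loss is unrelated to reintervention. The power gain from time itself is small: 1 to 3 points over chi-square on all 116 under the assumed scenarios.

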Appendix A—Data Instrument

Study ID: _____

Demographics:

Age_____ Gender: M F

Underlying diagnosis:

Pancreatic CA Cholangio CA Other (specify)_____

Additional clinic data:

Serum bilirubin (mg/dL) _____

Serum WBC_____

Prior cholecystectomy Y N

Cholangiographic and technical procedure data:

Stricture length at ERCP: _____cm

Stricture extending to ampulla: Y N

Endoscopic ampullary mass present: Y N

Stricture involving cystic duct takeoff Y N indeterminate

Randomization: C-SEMS U-SEMS

Follow-up:

Day 1 adverse events: pancreatitis cholangitis cholecystitis perforation none

Day 30 (and at each 30 day interval thereafter):

Patient alive: Y N If deceased, days from stent placement until death: ____

Repeat ERCP since stent placement: Y N

Percutaneous biliary drainage since stent placement: Y N

Surgical biliary bypass since stent placement: Y N

Surgical, endoscopic, or percutaneous gallbladder interventi

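### The additional logistic regression for predictors of stent failure names no sparse-data method or short covariate list, though only about 12 to 17 failures are expected (minor; Fisher's tests unaffected)

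*Combined protocol and SAP*

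**What the plan says.** The section on sample size and planned statistical analysis gives the confirmatory work to Fisher's "exact test will be used to assess the statistical significance in proportion of primary and secondary study outcomes". It then adds a regression: "Additional univariate and multiple variable logistic regression analysis will be used to identify potential predictors of stent failure, to be reported including odds ratio", with 95% confidence intervals. The section closes: "A two-sided P value of <0.05 will be the threshold for statistical significance in all cases".

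It names no estimator, no rule for an empty cell, no covariates and no limit on their number. Appendix A records ten baseline or procedural items that could serve as predictors besides stent type: age, gender, diagnosis, bilirubin, white cell count, prior cholecystectomy, stricture length, extension to the ampulla, ampullary mass and cystic duct involvement. Diagnosis and cystic duct involvement each have three levels; the latter reads "Stricture involving cystic duct takeoff Y N indeterminate".

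The design figures are in the same section. Retrospective data gave a "long-term 25% failure rate of U-SEMS and 0% failure rate of C-SEMS". The sample size follows: "Assuming a somewhat more conservative estimate of durability rates, a sample size of 96 patients (48 per treatment arm"), and then "Also anticipating a 20% rate of dropout/loss to follow-up, the goal would be to enroll and randomize 116 total patients in the study".

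**The concern.** Logistic regression depends on the number of events, not the number of patients. If covered stents do as well as the sponsor hopes, failures will be few and almost all in one arm. Two difficulties follow.

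- If one arm has no failures, the maximum likelihood odds ratio for stent type, the one randomised predictor, runs to zero. Software then prints a huge standard error and a p value near 1. The paper could show that beside a clearly significant Fisher's test on the same data.
- With many covariates and few events, maximum likelihood pushes odds ratios away from 1 and may fail to converge.

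A third issue does not depend on the estimator. The plan's threshold also covers the predictor search, so a chance association among ten candidates could be declared significant.

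**Working it through.** **Inputs.** From the sample size section: 48 per arm needed, 116 randomised (58 per arm), a 20-point difference, 80% power, two-sided 0.05, and cited rates of 25% and 0%. The planning rates are not stated, so 25% v 5% is an assumption, tested in step 1.

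**1. Does 25% v 5% reproduce 48 per arm?**
- Pooled variance: [1.960 × √(2 × 0.15 × 0.85) + 0.842 × √(0.25 × 0.75 + 0.05 × 0.95)]² / 0.20² = 48.8, so 49.
- Unpooled variance: (1.960 + 0.842)² × (0.1875 + 0.0475) / 0.04 = 46.1, so 47.

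The plan's 48 lies between. By the pooled formula 24% v 4% also comes close (47). Pairs of 20% v 0% (35), 30% v 10% (62) and 25% v 0% (27) do not.

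**2. Expected failures** = n per arm × (sum of the two rates).

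| Rates | 48 per arm | 58 per arm |
|---|---|---|
| 25% v 0% | 12.0 | 14.5 |
| 25% v 5% | 14.4 | 17.4 |
| 25% v 25% | 24 | 29 |

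The 58 column assumes that all 116 are evaluable. After the planned 20% loss, 116 × 0.8 = 92.8 remain, giving 11.6 to 13.9 failures in the first two rows. All Appendix A items with stent type need 13 parameters, or about 12/13 = 0.9 to 17.4/13 = 1.3 failures per parameter.

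**3. Chance of no failures in the covered arm** = (1 − rate)^n.

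| True covered-stent rate | 48 per arm | 58 per arm |
|---|---|---|
| 0% | certain | certain |
| 2% | 38% | 31% |
| 5% | 8.5% | 5.1% |

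At 25% with 48 per arm it is about one in a million.

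**4. Results at 12/48 v 0/48.**
- Fisher's exact test: p = 0.0002.
- Maximum likelihood with Wald inference: a standard routine stops at a log odds ratio of −22.5 with a standard error of about 11,469, p = 0.998.
- Maximum likelihood with a likelihood-ratio test: chi-square 2 × (36.17 − 26.99) = 18.36 on 1 df, p = 0.00002. The upper 95% limit is 0.136, but there is no finite point estimate.
- Firth: odds ratio (0.5 × 36.5)/(48.5 × 12.5) = 0.030, profile 95% CI 0.0002 to 0.24, p = 0.00008.

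**5. Adding covariates.** The true stent log odds ratio at 25% v 5% is ln[(0.05/0.95)/(0.25/0.75)] = −1.85 (odds ratio 0.16). Simulation used 1,500 trials per setting, 48 per arm, with covariates independent and unrelated to outcome. The documents give no covariate frequencies, so these are assumed (binary items at 30% or 50%).

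| Covariates besides stent type | Maximum likelihood not finite | Mean log OR, maximum likelihood (finite fits) | Mean log OR, Firth |
|---|---|---|---|
| 0 | 8.6% | −1.88 | not listed |
| 2 | 9.6% | −1.88 | −1.82 |
| 4 | 10.9% | −1.94 | −1.83 |
| 10 | 12.5% | −2.29 | −1.84 |

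With 58 per arm and ten covariates the means are −2.19 (maximum likelihood) and −1.83 (Firth). In the ten-covariate model at 48 per arm, the false-positive rate per unrelated covariate is 8.1% by likelihood ratio and 4.8% by Firth.

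The 12.5% is not robust. It treats diagnosis and cystic duct involvement as single columns. Coding both with three levels, with some rarer binary items, gives 44% or 57% under two other sets of assumed frequencies. The 44% also counts fits that diverged; its mean log odds ratio is −2.37. The fair range at 48 per arm is about 12% to 60%. At 25% v 25%, with the first coding, it is 0 to 0.2%.

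**6. False predictors.** For ten unrelated candidates tested one at a time, 1 − 0.95^10 = 40%. Simulated at 25% v 5% with 48 per arm: Wald 34%, likelihood ratio 45%, Firth 40%.

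**The case against.** The regression is explicitly additional and looks only for potential predictors. Fisher's test carries the primary and secondary comparisons and handles an empty arm without difficulty. The plan commits to neither maximum likelihood nor Wald inference, nor to entering every Appendix A item at once; its wording would allow Firth or profile intervals. The sample size moves away from the cited 0%, and at the implied 5% an empty arm is unlikely. The Background also reports that "a recent meta-analysis demonstrated no clear advantage of C-SEMS vs U-SEMS"; if the arms are alike, failures are plentiful enough for the estimation problem almost to vanish.

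Most of this stands, and it keeps the point minor. A reader might infer that the trial's main result is at risk, that an empty covered arm is the expected outcome, or that the plan mandates a ten-covariate maximum likelihood model. The documents support none of these.

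What remains is that the hypothesis favours covered stents, and the analysis should work if the hypothesis is true. An unqualified logistic regression is naturally read as ordinary maximum likelihood. Choosing the estimator and covariates after seeing an empty cell is the discretion that a plan should remove. The plan does not call the analysis exploratory, and it gives it the same threshold as the primary test.

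**Conclusion.** This is a minor point and a cheap improvement; the planned Fisher's exact tests and the sample size are unaffected.

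- An empty covered arm leaves no finite maximum likelihood odds ratio for stent type. The size of this risk depends on a true covered-stent failure rate that nobody yet knows.
- Bias matters only in a large model: trivial with up to four covariates, about −2.2 to −2.3 against −1.85 with ten. The frequency of non-finite fits in a full Appendix A model, about 12% to 60%, rests on assumed frequencies and coding.
- The roughly 40% chance of a false predictor assumes ten unrelated candidates, each tested at 0.05. It might be inferred that a better estimator cures this. It does not; only limiting the claims and the candidate list does.

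Nor should Firth's small mean bias with ten covariates be read as permission for a large model. Power for stent type at 48 per arm fell from 78% with two covariates to 70% with full Appendix A coding under assumed frequencies. A short list is still needed.

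**What to change.** In the section on sample size and planned statistical analysis, replace the sentence on logistic regression with:

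> Univariate and multivariable odds ratios for predictors of stent failure will be estimated by Firth-penalised logistic regression with profile penalised-likelihood 95% CIs and p values (not Wald). The multivariable model will contain stent type and a short list of baseline or procedural covariates fixed before data review. All predictor analyses are exploratory.

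In the sentence on the significance threshold, replace the last three words with: for the Fisher's exact comparisons of primary and secondary outcomes.

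The investigators should choose the list and write it into the plan. It need not be confined to Appendix A: stent length, left to the proceduralist under Procedure, is an evident candidate that does not appear in the appendix as available.

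The cost is three sentences and one phrase, plus agreement on the list. No more patients are needed, and Firth routines are standard. Odds ratios will shrink slightly towards 1, fewer predictors will be adjusted for at once, and predictors will no longer be declared significant.

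### The logistic model for predictors of stent failure ignores time at risk and has no rule for deaths, so features tied to short survival are biased toward looking protective if deaths count as non-failures

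*Combined protocol and SAP*

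**What the plan says.** Under Sample size and planned statistical analysis, after Fisher's exact test for the study outcomes, the plan adds: "Additional univariate and multiple variable logistic regression analysis will be used to identify potential predictors of stent failure", with results "to be reported including odds ratio and 95% confidence intervals". The significance threshold is two-sided 0.05 throughout. The candidate predictors are not listed; the likely ones are the baseline fields in Appendix A (age, sex, diagnosis, bilirubin, white cell count, prior cholecystectomy, stricture and ampullary findings).

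The outcome in Major treatment outcomes is a yes/no event: "Performance of repeat ERCP, percutaneous biliary drainage, or surgical biliary bypass for palliation of persistent or recurrent biliary obstruction". The Objectives say "Compare the rate of long-term stent failure, defined as need for repeat biliary intervention (endoscopic, percutaneous, or surgical", without saying how long is long-term. The Follow-up section says "Follow-up will occur every 60 days by review of the electronic medical record or patient self-report" and gives no end date or common duration; the form says "Day 30 (and at each 30 day interval thereafter".

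Appendix A records vital status and "If deceased, days from stent placement until death", but the analysis section makes no use of either. The visible reintervention items are of the form "Repeat ERCP since stent placement: Y N". Nothing says whether a patient who dies without reintervention is a non-failure or part of the anticipated 20% dropout.

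**The concern.** A logistic model of failed yes/no puts a patient who died at one month with an open stent in the same class as one whose stent stayed open for eighteen months. In inoperable malignant obstruction, time at risk is largely set by death. Randomization balances expected survival between the stent arms. It does not balance it between levels of diagnosis, age, bilirubin or white cell count. A feature that shortens survival and does nothing to the stent therefore lowers the chance of ever having a reintervention, and its odds ratio falls below 1.

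The stake is interpretation. An odds ratio published as a predictor of stent failure would be read as saying in whom a stent lasts, when part of it reflects who dies sooner.

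**Working it through.** **The plan's own figures.** There is none for the predictor analysis, so the trial's size sets the scale. For 25% v 5%, a pair consistent with the planned 20-point difference, the two-sided 0.05, 80% power formula gives n per arm = [1.96√(2×0.15×0.85) + 0.842√(0.25×0.75 + 0.05×0.95)]² / 0.20² = 48.8, or 49. For 24% v 4% it gives 47. These bracket the stated 48 per arm (96 in total). The 25% v 5% pair has a pooled failure risk of (25 + 5)/2 = 15%, or 96 × 0.15 = 14.4 failures.

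**Assumptions not in the documents.** Constant hazards; a binary feature splitting 96 patients 48 v 48; the feature changes the death hazard only; deaths without reintervention count as non-failures; median survivals of 4 v 10, 5 v 9 and 6 v 9 months.

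**Step 1, follow-up to failure or death.** With failure hazard λ and death hazard μ = ln 2 / median, the risk of ever failing is λ/(λ+μ) and the odds are λ/μ. With λ equal in both groups it cancels, so the odds ratio is the ratio of medians: 4/10 = 0.40, 5/9 = 0.56, 6/9 = 0.67. The true hazard ratio for the stent is 1 in each case.

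**Step 2, a 12-month cap.** The risk is λ/(λ+μ) × [1 − exp(−12(λ+μ))]. For 4 v 10 months, μ = 0.1733 and 0.0693 per month. With λ = 0.03 the risks are 0.135 and 0.210, and the odds ratio is 0.58 from unrounded risks. The cap shrinks the bias but does not remove it. For 6 v 9 months at 15% pooled failure the capped risks are 0.137 and 0.163, odds ratio 0.81.

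**Step 3, false-positive rates** (simulated, no true effect on the stent, two-sided 0.05):

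| Median survival, months | Logistic, 3%/month failure, followed to death | Logistic, 15% pooled, followed to death | Logistic, 15% pooled, 12-month cap | Cause-specific test |
|---|---|---|---|---|
| 4 v 10 | 43% | 30% | 12% | about 5% |
| 5 v 9 | 22% | 15% | 7% | about 5% |
| 6 v 9 | 14% | 10% | 6% | about 5% |

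A hazard of 3%/month followed to death implies pooled failure of 22.5%, 22.9% and 24.3%, close to the 25% that the plan cites for uncovered stents alone. The 15% columns therefore fit the trial better.

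**Step 4, when the direction changes.**
- *The feature also harms the stent.* The odds ratio is then (failure hazard ratio) × (ratio of medians). For 6 v 9 months a failure hazard ratio of 9/6 = 1.5 gives exactly 1, and a larger one gives an odds ratio above 1.
- *Deaths are excluded.* The odds become (risk of failure by 12 months) / (probability of being alive and failure-free at 12 months). Take medians of 4.5 v 9 months and λ = 0.0253, which gives 15% pooled failure at 12 months. Short survivors: 0.125/0.116 = 1.07. Long survivors: 0.175/0.293 = 0.60. The odds ratio is about 1.8, so the harmless feature now looks harmful.

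**The case against.** A reader might infer that every marker of short survival will look protective. The documents do not support that. It fails if the marker also raises the failure hazard enough, and it fails if deaths are removed as dropout, on which the plan is silent. Nor is it certain in a single trial: for 6 v 9 months at 96 patients and 15% pooled failure, the estimated odds ratio falls below 1 in 71% of simulated trials.

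The size is also open to challenge. Every survival figure is assumed, an even split with a 2.5-fold survival ratio is a favourable case, and nothing shows that bilirubin or stricture features separate survival that far. With a 12-month cap, two of the three error rates are close to nominal. All of this stands. What remains is that the plan sets no cap, and that with about 14 failures a rejection rate near 5% is compatible with a biased estimate, such as 0.81.

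The odds ratio is not meaningless. The Background sets the goal as drainage lasting for the patient's lifetime, and for that goal death with a working stent is a success. The odds ratio then describes who needs reintervention before death. This stands, but the hypothesis also concerns durability, and the plan's label of predictor of stent failure invites that reading.

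It would also be too strong to say that the form cannot time a reintervention. The available text of Appendix A breaks off, so a date field may follow. Repeated yes/no items already bracket the event between visits, and the medical record is under review anyway.

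Finally, one might extend the point to the main result. The plan is equally silent on deaths in the Fisher comparison, but there randomization balances expected survival between arms, so this argument does not carry over.

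**Conclusion.** The concern holds in a limited form. Followed as written, the predictor analysis mixes survival with stent durability across features that were not randomized, and nothing else in the plan separates them. If deaths without reintervention count as non-failures, features associated with short survival are biased toward odds ratios below 1: 0.40 to 0.67 for the assumed survival pairs with follow-up to death, and closer to 1 with a 12-month cap. At a failure risk in line with the planning figures, the false-positive rate is about 10% to 30% uncapped and 6% to 12% capped, against about 5% for a cause-specific test. The direction depends on the unstated rule for deaths, and the size depends on survival differences that the documents do not give. The analysis is secondary and exploratory; the primary comparison and the sample size are unaffected. The change should be made because it is cheap and gives a better answer to the question asked.

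**What to change.** Replace the logistic sentence with a cause-specific Cox regression of time from stent placement to first reintervention, censoring at death or last contact, with treatment arm in the model and a penalized fit if events are few. Report hazard ratios with 95% confidence intervals. Beside them, report the cumulative incidence of reintervention with death as a competing event, since the hazard ratio alone does not give the probability of needing reintervention. If an odds ratio is kept, state how deaths are classified and describe it only as the chance of reintervention before death. A fixed window alone would reduce the bias but not remove it.

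Record the date of first reintervention from the medical record already being reviewed, if the form does not already capture it. Reconcile the 60-day interval in the Follow-up section with the 30-day interval in Appendix A.

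The cost is a short rewording of the analysis section, at most one field on the form, and abstraction of dates for the patients who have a reintervention. Hazard ratios replace odds ratios as the main predictor measure.
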